### **3.4 Exclusion Criteria**

Exclusion criteria were selected to enhance safety and adherence. All subjects meeting any of the exclusion criteria at baseline will be excluded from participation.

1. Type 1 diabetes mellitus
2. Insulin treatment
3. Ketosis-prone diabetes
4. Previous diabetic ketoacidosis

5. Known peripheral vascular disease or history of lower limb amputations
6. History of Fournier's gangrene or skin and soft tissue infections of the perineum
7. Recurrent or severe urinary tract or genital mycotic infections, or history of genitourinary infection within 2 weeks prior to informed consent
8. Known allergic reaction to empagliflozin or other SGLT2 inhibitor
9. Significant renal impairment (estimated Glomerular Filtration Rate < 45 ml/min/1.73m^2\*\*)
10. Dialysis or kidney transplant
11. Renal artery stenosis
12. Alanine aminotransferase or aspartate aminotransferase above 3x upper limit of normal
13. Significant change in weight ( $\geq 10\%$  in the preceding 6 months)
14. Treatment with anti-obesity drugs
15. Previous bariatric surgery or other gastrointestinal surgeries that induce chronic malabsorption
16. Treatment with systemic glucocorticoids
17. Blood dyscrasias or clinically significant anaemia (Haemoglobin < 10 g/L)
18. Cancer within the last 5 years (except basal cell carcinoma)
19. Medical condition likely to limit survival to less than 3 years
20. Uncontrolled thyrotoxicosis, untreated hypothyroidism
21. Any ongoing acute medical illnesses
22. Hospitalization within 1 month prior to enrolment
23. Nursing mothers
24. Pregnancy, currently trying to become pregnant, or of child-bearing potential and not practicing an acceptable method of birth control or do not plan to continue using this method throughout the study
25. Excessive alcohol intake (> 1 unit per day for women and > 2 units per day for men)
26. History of drug abuse
27. Pancreatic insulin deficiency from any cause (history of pancreatitis, pancreatic surgery)
28. Known intolerance or allergic reactions to empagliflozin or other SGLT-2 inhibitors
29. Current participation in another clinical trial, or ingestion of investigational drug in another trial within 30 days prior to enrolment.
30. Chronic liver disease:
  - Hepatitis B
  - Hepatitis C
  - Autoimmune hepatitis
  - Hemochromatosis
31. Presence of any non-DN renal glomerular disease  
(e.g. IgA nephropathy, lupus nephritis, membranous glomerulonephritis, focal segmental glomerular sclerosis)
32. Any previous organ transplantation
33. Any factors likely to limit adherence to interventions (e.g. dementia; alcohol or substance abuse; history of unreliability in medication taking or appointment keeping; significant concerns about participation in the study from spouse, significant other or family members)
34. Failure to obtain informed consent from participant

\*\*MDRD formula: eGFR (ml/min) = 175 x [Creatinine (umol/L)/88.4]-1.154 x [age]-0.203 x 0.742 [if patient is female]  
Ann Intern Med. 1999 Mar 16;130(6):461-70. Am J Kidney Dis. 2002 Feb;39(2 Suppl 1):S1-266.

### 3.5 Subject Replacement

There will be no replacement of subjects who drop out of the study.

## **4 STUDY DESIGN**

In this single-centre, open-label study, 40 adults with DN will be recruited over 2 years. Following screening and baseline metabolic evaluations, eligible subjects will be treated with empagliflozin for 30-days and re-assessed.

### **4.1 Randomisation and Blinding**

No randomization or blinding will be performed as the response to empagliflozin is stereotypical and the measured parameters are objective and thus not subject to observer bias.

### **4.2 Contraception and Pregnancy Testing**

There are no adequate data from the use of empagliflozin in pregnant woman. Therefore, pregnant women cannot participate in this study. Female subjects of childbearing potential will be tested for pregnancy using urine pregnancy test kits during their screening (**Visit 1**) and dosing visits (**Visit 2**). Sexually active women of childbearing potential must use a reliable method of birth control while participating in this study. Reliable methods of birth control are considered to be abstinence (not having sex), oral contraceptives (the pill), intrauterine device (IUD), DepoProvera, Norplant, tubal ligation (tubes tied) or vasectomy of the partner. An acceptable although less reliable method, involved the careful use of condoms and/or a spermicidal foam or gel along with a diaphragm, cervical cap, or sponge. Study subjects would be encouraged to discuss this issue further with their doctor if they have any questions.

#### 4.3 Study Visits and Procedures

**4.3.1** Patients who meet inclusion criteria and do not meet any of the exclusion criteria will be invited to participate during their visit to the DMC at SGH by the PI, Co-Is or their managing physician. Interested patients will be scheduled for their first study visit (**Visit 1**) within **28 days** at SGH CTRC.

#### 4.3.2 VISIT 1: Informed Consent and Screening

Written informed consent will be taken by the principal investigator, co-investigators or study team members assigned by the PI. After consent has been taken, study procedures in **Table 1** will be performed. The PI, Co-I or study team member(s) assigned by the PI will review screening results to determine whether subjects are eligible to continue with the study. Information regarding all concomitant therapy taken by the patients will be collected.

**Table 1. Study Procedures**

	Visit 1	Visit 2	Visit 3
	Consent & Screening	Dosing & Metabolic Evaluation	Post-treatment and Final Visit
Administrative			
Informed consent	X		
Inclusion/Exclusion criteria	X		
Dispense Medication		X	
Monitoring of drug compliance			X
Clinical Procedures/Assessment			
Fasting ( $\geq 8$ hours)		X	X
Medical History/Assessment	X		X
Drug History	X		X
Adverse Effects Monitoring			X
General Physical Examination	X		X
BP/Pulse	X		X
Weight (triplicate) *	X		X
Height (triplicate) *	X		
Hip/Waist Circumference (triplicate) **	X		X
Indirect Calorimetry ***		X	X
Laboratory Procedures			
HbA1C	X		
Fasting Glucose		X	X
Full Blood Count	X		
Potassium	X		X

Creatinine	X		X
eGFR Calculation	X		X
Lipid Panel		X	X
Urine $\beta$ HCG (female of child bearing potential)	X	X	
ALT	X		X
AST	X		X
Metabolomic Profiling		X	X
Urine ACR	X		X
Urine PCR		X	X

\* Weight will be measured in light clothing to the nearest 0.1 kg on a balance scale and height with a stadiometer three times and then averaged

\*\* Waist circumference will be measured from the inferior margin of the last rib and hip circumference measured at the crest of the ileum to the nearest 0.1 cm three times and averaged

\*\*\* Indirect calorimetry using a canopy hood will be performed for 30 minutes for measurement of basal energy expenditure, CO2 production and O2 consumption

ALT = Alanine Transaminase

AST = Aspartate Transaminase

## SAMPLE COLLECTION

A total of 37ml (~8 teaspoons) of blood and 32ml (~7 teaspoons) of urine will be collected for the entire study. During visit 1 (Screening), 11ml (~2 teaspoons) of blood and 6ml (~1 teaspoon) of urine will be collected. During visit 2 (Dosing visit), 13ml (~3 teaspoons) of blood and 11ml (~3 teaspoons) of urine will be collected. During visit 3 (Post-treatment and final visit), 13ml (~3 teaspoons) of blood and 15ml (~3 teaspoons) of urine will be collected. If female subjects are actively menstruating at the time of study visit, urine tests will not be sent for biochemical or metabolomics analysis.

Blood and urine samples for laboratory testing at the clinical laboratory (Table 1) will be despatched for immediate analysis. Blood and urine samples for metabolomic profiling will be stored in the SGH CTRC at -80°C, and then sent to Duke-NUS laboratory for batch analysis.

Informed consent will be taken from participants regarding storage of biological materials. The blood and urine specimens will be coded and stored for future research if participants consent to this. The blood specimens will not be transferred out of Singapore.

Subjects who developed drug-related adverse reactions may require additional blood and urine taken for clinical assessment. The estimated amount required for these additional assessments are 10 ml (~2 teaspoons) of blood and 10 ml (~2 teaspoons) of urine.

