## Study aims

The aim of our proposed study is to **examine the state of fuel metabolism in patients with DN both before and after the use of SGLT-2i**. We anticipate that 30 days of treatment with the SGLT-2i empagliflozin will induce a shift in fuel metabolism in subjects with DN.

Our hypothesis is that dysregulated fuel metabolism is a major driver of diabetic nephropathy. We propose that the beneficial effect of SGLT-2i in DN is related to changes in fuel metabolism. Our anticipated outcomes include reversal of many of the metabolomics findings reported in DN. We expect decreased fasting glucose and elevated serum ketones, as previously reported. We also predict reductions in the levels of short-chain acyl-carnitines, increased C4-OH and long-chain acyl-carnitines as well as reductions in urinary organic acid excretion. Unfortunately, the scope of this proposal is too short to expect significant changes in albuminuria, although this will be assessed. If completed successfully, this project will help to link changes in mitochondrial fuel metabolism with the beneficial effects of the SGLT-2i class of drugs.

Our goals are to better understand the contribution of fuel metabolism to the development of DN, and to determine if changes to fuel metabolism can have a positive impact on this disease.

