### B) Metabolomic Profiling

Metabolomic profiling of lipids, acylcarnitines (ACs), organic acids and ketones will be measured using liquid and gas chromatography and tandem mass spectrometry (LC-MS/MS and GC-MS/MS) at the Duke-NUS metabolomics laboratory. Metabolomic analysis will be performed on serum (acyl-carnitines, amino acids and organic acids) as well as urine (organic acids).

ACs represent intermediaries of metabolic fuel oxidation and provides a “snap-shot” of *in vivo* metabolism at the cellular level. The measurement of the various long-, intermediate-chain ACs provide an indicator of fatty acid oxidation efficiency. Ceramides are toxic lipid intermediaries that are implicated in the pathogenesis of insulin resistance. Lactate, pyruvate, succinate, fumarate, malate, alpha-ketoglutarate and citrate are organic acids involved in TCA cycle activity. Beta hydroxybutyrate is a ketone which will also be measured with the organic acids.

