#### 4.3.3 VISIT 2: Initiation of Study Drug

Subjects who satisfy the inclusion and exclusion criteria will return to the CTRC within the next **14 days** for **visit 2** to receive the study drug, empagliflozin. Empagliflozin 10mg daily is to be taken orally for  $30 \pm 7$  days. Subjects will take the first dose of empagliflozin under supervision of the clinical research coordinator at SGH CTRC.

Patients will be instructed to take empagliflozin once daily with water. To ensure a dose interval of about 24 hours, the medication should be taken at the same time every day, with or without food. If a dose is missed by more than 12 hours, that dose should be skipped and the next dose should be taken as scheduled. No double doses should be taken, and dose reductions are not permitted.

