#### 4.3.4 VISIT 3: 4-Week Post-Treatment and Final Visit

**Visit 3** will take place  **$30 \pm 7$  days** from Visit 2. Subjects will be assessed to quantify changes in metabolic fuel utilization after treatment with empagliflozin. These changes are determined based on metabolomic profiling of acyl-carnitines, organic acids and amino acids and indirect calorimetry measurements. The list of procedures performed is listed in **Table 1**.

Subjects will take their final dose of study medication on the day of visit 3. Subjects will be asked to bring all trial medication containers (with or without any remaining tablets) with them to visit 3. Subjects who forget to return trial medication containers will be asked to bring them at a separate visit. The tablets will be counted by the PI, Co-I or study team members and compliance will be calculated according to the formula:

$$\text{Compliance (\%)} = \frac{\text{Number of tablets actually taken since visit 2}}{\text{Number of tablets which should have been taken in the same period}} \times 100\%$$

In addition, study subjects will be asked to fill up a Subject Treatment Diary to record the number of doses of empagliflozin 10mg taken. The Subject Treatment Diary will be reviewed by the PI, Co-I or study team member at visit 3.

The study drug will be discontinued upon completion of visit 3, and any remaining study drug tablets will be returned to the study team.

Should study subjects misplace any empagliflozin 10mg tablets between visit 2 and visit 3, the exact number of misplaced tablets will be resupplied to them by the study team.

Study drug will be discontinued for subjects upon occurrence of any adverse drug reaction to empagliflozin.

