## **6 TREATMENT**

### **6.1 Rationale for Selection of Dose**

Dosage of empagliflozin is similar to that used for the treatment of type 2 diabetes mellitus in clinical practice. Eligible subjects will be given empagliflozin 10mg once daily to be taken orally for 30 ± 7 days.

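### Not sending urine when a woman is menstruating, with no repeat or rebooking, needlessly loses paired urine data that the existing visit windows would let the site keep

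*Protocol*

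**What the plan says.** The rule is one sentence under Sample Collection (Protocol section 4.3): "If female subjects are actively menstruating at the time of study visit, urine tests will not be sent for biochemical or metabolomics analysis". Nothing else in the protocol provides for a repeat urine, a later collection or a moved visit.

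Table 1 fixes when each urine outcome is measured:

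- Urine ACR: Visits 1 and 3.
- Urine PCR: Visits 2 and 3.
- Metabolomic profiling: Visits 2 and 3. The Metabolomic Profiling text includes organic acids in urine.

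Urine results belong to what the study sets out to show. The Study aims list, among the predicted changes, "as well as reductions in urinary organic acid excretion". Section 9.2 compares baseline with post-treatment values by a paired t-test.

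The visit windows are:

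- Visit 1 (section 4.3.1): "Interested patients will be scheduled for their first study visit (Visit 1) within 28 days at SGH CTRC".
- Visit 2 (section 4.3.3): subjects "will return to the CTRC within the next 14 days for visit 2 to receive the study drug".
- Visit 3 (section 4.3.4): 30 ± 7 days after Visit 2. The treatment period carries the same tolerance (section 6.1): "Eligible subjects will be given empagliflozin 10mg once daily to be taken orally for 30 ± 7 days".

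**The concern.** Withholding urine that may be contaminated with blood is sound. The weakness is that the rule stops there. Each urine outcome has exactly one baseline and one follow-up value, so one unsent sample removes that woman from the paired comparison, and no later analysis can recover a sample that was never sent. The schedule already contains days on which a usable sample could be taken, yet the text directs omission and not a different day. At stake is some precision for urinary organic acids, PCR and ACR in a study of 40.

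**Working it through.** **The plan's own figure.** Section 9.1 needs 40 subjects and assumes that 1 in 3 fail screening: 40 / (1 − 1/3) = 60 to be screened, as stated. The 40 itself cannot be reproduced, because no effect size, standard deviation or power is given.

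**Which pair is lost, from Table 1.**

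| Menstruating at | ACR pair (V1, V3) | PCR pair (V2, V3) | Urinary organic acid pair (V2, V3) |
|---|---|---|---|
| Visit 1 | lost | kept | kept |
| Visit 2 | kept | lost | lost |
| Visit 3 | lost | lost | lost |

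**Chance that a menstruating woman loses her PCR and organic acid pairs.** Assumptions: a 28-day cycle, B consecutive bleeding days, Visit 2 on a random cycle day, and Visit 3 equally likely on each of days 23 to 37 after Visit 2 (37 − 23 + 1 = 15 days).

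P(lost) = P(bleeding at V2) + P(bleeding at V3) − P(both) = 2B/28 − P(both).

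Relative to a 28-day cycle the gap is shifted by s = −5 to +9 days, and the two bleeding spells overlap on max(0, B − |s|) days. For B up to 6 these overlaps sum to B², so P(both) = B² / (15 × 28) = B²/420.

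- B = 4: 8/28 − 16/420 = 0.286 − 0.038 = 0.248
- B = 5: 10/28 − 25/420 = 0.357 − 0.060 = 0.298
- B = 6: 12/28 − 36/420 = 0.429 − 0.086 = 0.343

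A simulation with cycle length varying as Normal(28, 3) gives 0.25, 0.30 and 0.35. With cycles of 24 to 35 days and 3 to 7 bleeding days the range widens to 0.15 to 0.49.

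These figures do not apply to ACR, whose baseline is Visit 1. With a 28-day cycle and Visit 1 placed 1 to 14 days before Visit 2, the same enumeration gives 0.27, 0.34 and 0.40 for 4, 5 and 6 bleeding days.

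**Pairs lost.** The protocol does not give the number of menstruating women. Assuming 4 to 12 of 40:

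- low end: 4 × 0.25 = 1.0 pair
- high end: 12 × 0.35 = 4.2 pairs

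So about 36 to 39 of 40 PCR and organic acid pairs remain.

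**What that costs.** For an unchanged standard deviation of the differences, the standard error grows by √(40/39) = 1.013 to √(40/36) = 1.054, that is by about 1 to 5%. As a benchmark only, since the protocol states no power: a standardised paired difference of 0.454 has 80% power with 40 pairs (two-sided 0.05), about 79% with 39 and about 76% with 36.

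**Can the loss be avoided inside the windows?** A window longer than one bleeding spell must contain a bleeding-free day. Over any stretch no longer than the cycle there are at most B bleeding days. For cycles of at least 21 days and spells of up to 8 days, this leaves:

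- Visit 2: at least 14 − 8 = 6 free days
- Visit 3: at least 15 − 8 = 7 free days
- Visit 1: 28 days, so free days always exist

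Each visit can be placed whatever day the previous one fell on, so no pair need be lost to this rule under these assumptions, and no window has to be widened. Turnaround of screening results will shorten the usable part of the Visit 2 window, but there is room for it.

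**The case against.** The strongest case against is that this is a scheduling preference. The quality rule is right, nothing in the protocol forbids choosing a visit day around menses, and a site procedure could hold the instruction. That is fair as to weight. It does not remove the point: the protocol does speak to the situation, and what it prescribes is omission.

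The size also rests wholly on assumptions. Ages run from 21 to 65, and no sex ratio or menopausal status is given, so the loss could be about one pair. The Study aims themselves expect no significant change in albuminuria in so short a study, so lost ACR pairs matter less than lost organic acid pairs.

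Nor is rebooking quite free. Bleeding may be noticed only when a fasted woman arrives. The last dose is tied to Visit 3, so moving that visit moves her treatment length, though only within the ± 7 days already allowed. Section 9.1 speaks of an effect at 23 to 30 days, while the window runs to 37.

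Stronger readings that a reader might infer are not supported:

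- *Any menstruating visit costs every urine outcome.* Only Visit 3 does, by Table 1.
- *The urine results are biased because only menstruating women drop out.* Each woman is her own control, and nothing in the documents links the chance of a visit falling on a bleeding day to her metabolic response.
- *Eligibility is undermined by a missing Visit 1 ACR.* Inclusion criterion 3 asks for two or more raised ACR or PCR measurements within a year and does not require the Visit 1 sample.
- *The no-replacement rule makes it worse.* Section 3.5 concerns dropouts, and these women stay in the study with their serum data.

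**Conclusion.** The point holds as a minor, cheaply avoided loss of paired urine data. Followed as written, the rule would cost about 25 to 35% of menstruating women their PCR and urinary organic acid pairs, assuming 4 to 6 bleeding days in a cycle of about 28 days and visits placed without regard to the cycle. With an assumed 4 to 12 menstruating women among 40, that is about 1 to 4 pairs and a standard error larger by roughly 1 to 5%. The consequence is modestly lower precision for one predicted outcome, urinary organic acids, and for PCR; ACR pairs are lost through Visits 1 and 3. Serum metabolomics and indirect calorimetry are untouched, and the study's main conclusions do not turn on it.

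**What to change.** Amend the sentence under Sample Collection along these lines: for women who menstruate, Visits 1, 2 and 3 are booked on non-menstruating days within the existing windows (28 days, 14 days and 30 ± 7 days). If bleeding is present on the day, the visit is rebooked within its window. Urine is omitted, and recorded as missing for this reason, only if that is not possible.

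Two conditions belong in the text. Baseline urine for PCR and organic acids must be taken before the first dose, which is given at Visit 2, so it is Visit 2 that moves. Visit 3 urine must be taken while the subject is still on treatment, because the drug stops on completion of that visit; a urine sample collected afterwards would not serve. Visit 1 must be included, since it supplies the only baseline ACR.

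The cost is a question about cycle timing at booking, an occasional rebooked visit (fasting, for Visits 2 and 3), and slightly more variation in visit day within the range already permitted. No window or laboratory procedure changes.

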## LABORATORY MEASUREMENTS

### A) Blood Chemistry

Screening and standard laboratory tests including full blood count, Potassium, Creatinine, ALT, AST,  $\beta$ -HCG (for female subjects of childbearing age), lipid panel, glucose and HbA1c will be measured using standard methods.

### B) Metabolomic Profiling

Metabolomic profiling of lipids, acylcarnitines (ACs), organic acids and ketones will be measured using liquid and gas chromatography and tandem mass spectrometry (LC-MS/MS and GC-MS/MS) at the Duke-NUS metabolomics laboratory. Metabolomic analysis will be performed on serum (acyl-carnitines, amino acids and organic acids) as well as urine (organic acids).

ACs represent intermediaries of metabolic fuel oxidation and provides a “snap-shot” of *in vivo* metabolism at the cellular level. The measurement of the various long-, intermediate-chain ACs provide an indicator of fatty acid oxidation efficiency. Ceramides are toxic lipid intermediaries that are implicated in the pathogenesis of insulin resistance. Lactate, pyruvate, succinate, fumarate, malate, alpha-ketoglutarate and citrate are organic acids involved in TCA cycle activity. Beta hydroxybutyrate is a ketone which will also be measured with the organic acids.

### C) Urine Protein Excretion

Urine ACR and PCR will be performed to quantify urine protein excretion.

#### 4.3.3 VISIT 2: Initiation of Study Drug

Subjects who satisfy the inclusion and exclusion criteria will return to the CTRC within the next **14 days** for **visit 2** to receive the study drug, empagliflozin. Empagliflozin 10mg daily is to be taken orally for  $30 \pm 7$  days. Subjects will take the first dose of empagliflozin under supervision of the clinical research coordinator at SGH CTRC.

Patients will be instructed to take empagliflozin once daily with water. To ensure a dose interval of about 24 hours, the medication should be taken at the same time every day, with or without food. If a dose is missed by more than 12 hours, that dose should be skipped and the next dose should be taken as scheduled. No double doses should be taken, and dose reductions are not permitted.

